Depression evaluation: All subjects will undergo a Structured Clinical Interview for DSM-IV (SCID) for the purposes of establishing a diagnosis of Major Depression (MDD). A history of depressive illness includes the length of the current episode of MDD, age of onset of the illness, prior duration of the illness, and number of episodes. Assessment of depressive symptoms will be based upon administration of the Hamilton Rating Scale for Depression (HAM-D-24-item). Other domains of baseline assessment will address issues thought to be important in understanding risk factors for LLD will be tabulated. High levels of inter-rater reliability will be maintained. For example, inter-rater reliability for the total HAM-D-24 score or the SCID diagnosis of depression has been excellent, as demonstrated by ICCs of 0.78 to 0.95. The age at depression onset will be determined using subjects' report, and medical records. We will stratify both groups by the age at onset with cut off at age 60 to examine the role of late vs. early onset in treatment response.

Comorbid anxiety and insomnia. Comorbid anxiety disorders and insomnia can be present and assessed at baseline and follow up.

Assessment instruments. All instruments have been selected because of their validation with geriatric patients in clinical trials, as well as their direct relevance to the posed hypotheses. They provide a comprehensive assessment of the severity of depression, medical comorbidity, cognitive and functional impairment, life satisfaction, and quality of life. The use of these instruments will enable the PI to compare results of the study to other investigations. Most instruments, except the cognitive tests and self-administered ones, will be administered by the PI or the co-investigator (Tables 2;4).

Measures of cognition (administered at baseline; repeated at 6 and 12 months, or upon early termination).

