8) Remission and naturalistic 6 month follow up: Subjects who achieve remission (HAMD<6) will be offered up to additional six months of continuation treatment with escitalopram to determine stability of remission, while memantine and placebo will tapered off. The goal of continuation treatment is to ensure stability of remission, and to optimize coping, cognition, physical functioning, and life satisfaction. Although subjects achieved remission, we will continue monitoring their safety every month during in-person visits monthly up to 12 months. The frequency of these visits is consistent with the clinical practice, where stable subjects are generally seen every 1-6 months. They will be also encouraged to contact the investigators if they experience worsening of depression or suicidal ideations. Subjects who do not remit during the acute treatment phase or relapse during the continuation phase will be offered treatment outside the protocol in the Geriatric Mood Disorders Clinic or other community clinics. They will be invited to come for the 6 and 12 month follow up to assess their progress and the patterns of response to treatment while tracking and controlling any changes in treatment.

Safety evaluations. Vital signs and body weight will be obtained at each visit, in addition to a 12-lead ECG at baseline, and if any cardiac complaints are present. The UKU Side Effect Rating Scale, a comprehensive rating scale for monitoring adverse events of psychotropic drugs will be collected at all visits. Laboratory assessment. A comprehensive baseline laboratory study is required to arrive at accurate differential diagnoses in "organic" and potentially treatable causes of depression or cognitive impairment. All laboratory tests and ECG assessments will be done at the UCLA CTSA center. Treatment compliance will be assessed by employing indirect measures of adherence, i.e., direct questioning of the patients and their available relatives, and returned pill count.

Decoding procedures. In case of emergency or adverse event, the blind will be broken for clinical management of the patient after the decision has been made to discontinue the patient from the study and final ratings have been obtained. The pharmacist will provide a patient randomization number and corresponding treatment assignment to the PI.

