In the end of the trial after unblinding procedures, the PI, in consultation with the patient's primary physician, will decide whether to continue the prescribed medications or switch to another antidepressant based on treatment response and tolerability. If a decision is made to discontinue both medications, they will be stopped and further observation for any withdrawal symptoms will be provided either by the patient's primary physician or the PI for two weeks following the discontinuation.

4.1 * Will you be providing results of any experimental tests that are performed for the study?

Yes - Complete Items 4.1.1 and 4.1.2

No

Not Applicable

4.1.1 You indicated in Item 4.1 that the research involves experimental tests. Please describe the tests, provide a rationale for providing participants with the experimental test results and explain what, how and by whom participants and their health care provider will be told about the meaning, reliability, and applicability of the test results for health care decisions.

4.1.2 Will tests be performed by a Clinical Laboratory Improvement Amendments (CLIA) approved lab?

Yes No

5.0 *Indicate how much time will be required of the subjects, per visit or contact, and in total for the study.

This study will require that the subjects complete up to 20 (twenty) visits in 12 (twelve) months to the study site during their participation. The time required for each visit are as follows:

- 1) Screening Procedures and Initial Visit (Screening / Visit 1): The initial visit will last approximately 2 ½ to 3 hours.
- 2) Baseline Diagnostic / Neuropsychological Evaluation Visit (Visit 2) will last approximately 2 hours.
- 3) Magnetic Resonance Imaging (MRI) Scans (2) : Subjects will be asked to lie still for about 60 minutes while the scan is taking place at baseline and at 12 weeks.
- 4) Positron Emission Tomography (PET) Scan: This examination will require approximately 2 hours for completion.
- 5) Follow-Up Visits (Visits 7-13, 15-20): Follow-up visits will occur weekly for the 4 weeks (6 visits), bi-weekly (every 2 weeks) for visits 7-14 (up to 6 month visits), and every month until the end of the study. Each visit will last approximately 30 minutes.
- 6) Final visit (Visit 14): The last visit will be approximately 2 hours.

6.0 *Statistics and Data Analysis: Describe the proposed statistical procedures or descriptive analyses for the study. If applicable, indicate how the sample size was determined.

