maximum amount taken was 2000 mg with full recovery. Interactions with other drugs: Drug-drug interactions are an important consideration in prescribing antidepressants for the elderly who often take multiple drugs metabolized through the liver and may have reduced hepatic metabolism. Serotonin release by platelets plays an important role in hemostasis. Epidemiological studies with case-control and cohort design that have demonstrated an association between gastrointestinal bleeding and SSRIs. Interaction at the level of liver enzymes becomes likely. In general, escitalopram appears to be less likely to cause important drug interactions than the other SSRIs. Escitalopram is unlikely to interact with lithium, carbamazepine, benzodiazepines, warfarin, or erythromycin. Escitalopram has low potential for interacting with most other drugs, including beta blockers, neuroleptics, lithium, and alcohol. The serotonergic syndrome has been reported in combined use of reversible MAOI, meclizolide, and linezolid, an antibiotic, which is a reversible non-selective MAOI. At least 14 days should be allowed between the administration of escitalopram and MAOI. Central serotonin syndrome could be lethal. Other potential adverse effects include discontinuation syndrome after abrupt discontinuation of escitalopram with symptoms of irritability, agitation, dizziness, sensory disturbances, and paresthesias that are usually self-limiting. Abnormal bleeding, hyponatremia, activation of mania, hypomania, or seizures might occur. Increased agitation and irritability may occur. All adverse events will be carefully monitored during each visit using the UKU Side Effect Rating Scale. If any serious medical complication occurs, the patient will be referred to their primary care physician.

Emergence of anxiety is a reported adverse effect of escitalopram use. This side effect occurred in two of our subjects, and required lowering the drug dose. If this occurs, dose and schedule adjustment of study medication, escitalopram, will be attempted and project staff will contact such subjects twice a week to evaluate their symptoms and monitor for emergent suicidal ideations. Relaxation tapes will be offered for use at night by subjects with insomnia. Sleep hygiene will be encouraged as well, with recommended walks in the evening and warm baths before bedtime. Subjects' relatives will be encouraged to be involved in the study to ensure subjects' safety and compliance.

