Risks associated with memantine. The following Adverse Drug Reactions have been accumulated in clinical studies with memantine since its introduction in the market. Body as a whole – general disorders: Common-Headache; Uncommon-Fatigue; Psychiatric disorders: Common- Somnolence; Uncommon- Confusion, Hallucinations; Not known-Psychotic reactions; Gastro-intestinal system disorders: Common-Constipation; Uncommon-Vomiting; Not known Pancreatitis; Central & Peripheral nervous system: Common-Dizziness disorders; Uncommon- Gait abnormal; Very rare-Seizures. Overdose. There have been very few cases of overdose. In the case of an overdose (a suicide attempt), for which the highest memantine dose has been reported, the patient survived an oral intake of up to 400 mg memantine with effects on the central nervous system (that is, restlessness, psychosis, visual hallucinations, proconvulsiveness, somnolence, stupor, and unconsciousness) that resolved without permanent sequelae. Treatment of overdosage should be symptomatic.

Risks associated with combination of memantine and escitalopram. Combination of memantine with escitalopram is commonly used in clinical practice with rare side effects including increased anxiety and sleep disturbances. Dose modification is typically sufficient to lower the rate of side-effects.

Discontinuation from the study will be considered if subjects experience. We will monitor blood pressure and pulse once a week in the first four weeks, and at every visit. If any changes on the baseline ECG signifying ischemia occur, we will obtain additional tests of cardiac enzymes to rule out myocardial infarction (MI) (e.g., CK-MB; troponin). [name] is a part of the consulting and the DSMB teams and has advised us on the following parameters for discontinuation from the trial if cardiovascular complications arise. These include:

- a. Any changes in subject's physical complaints of a potentially vascular nature (e.g., angina or chest pain, fainting, dizziness, arrhythmia); increase in pulse over 10 beats per minute from baseline or tachycardia over 120 beats per min, changes in BP over 20 mm Hg;
- b. Changes on ECG or in cardiac enzymes indicating cardiac ischemia or a new onset arrhythmia;
- c. The development of any severe side-effects on the UKU Side Effect Rating scale rated as 3 or greater.

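### The code-break rule places a discontinuation decision and final ratings before unblinding even in an emergency, and the application text gives no exception

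*Combined protocol and SAP*

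**What the plan says.** Section 10.1, item 4.0, under Decoding procedures, names the trigger: "In case of emergency or adverse event, the blind will be broken for clinical management of the patient". The same sentence then fixes the timing: "after the decision has been made to discontinue the patient from the study and final ratings have been obtained". The next sentence has the pharmacist pass the randomization number and treatment assignment to the PI.

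The only other mention of unblinding follows directly and concerns the end of the trial. The safety and withdrawal text (section 14.1, item 3.0; section 15.2, items 4.1 and 5.1) deals with dose reduction, referral, discontinuation criteria and reporting. It does not mention the code.

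**The concern.** Rating a patient before the code is known protects the outcome assessment from bias, and it is a sound default. The difficulty is that this rule applies the default to emergencies as well. Its two conditions are joined by *and*, and the second requires a patient who can be rated.

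The patients for whom an urgent code-break is most likely to be wanted are among those least able to be rated: someone who is confused, psychotic, stuporous or seizing. For them the condition cannot be met when the information is wanted, and the text offers no fallback. At stake is how soon a treating clinician can learn whether memantine is a possible cause. The type I error rate, the power and the treatment comparison are not affected.

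**Working it through.** No formula applies and the plan states no figure to reproduce. The check is whether the rule reaches emergencies, whether anything relaxes it, whether the plan foresees patients who could not meet it, and what the delay would withhold.

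1. **Does the rule reach emergencies?** Yes. The trigger clause names an emergency alongside an adverse event, and a single timing clause governs both. The stated purpose is clinical management, so the plan accepts that the assignment can matter to care.

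2. **Does other text relax it?** None in the application. Under Adverse events, section 14.1, item 3.0 provides for referral to the primary care physician after a serious complication. The general assurance there about protecting subjects does not mention the code. Section 15.2, items 4.1 and 5.1, sets out dose adjustment and discontinuation criteria. The remaining unblinding text is for the end of the trial.

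3. **Does the plan foresee patients who cannot be rated?** Yes. Section 14.1, item 3.0 lists for memantine "Uncommon- Confusion, Hallucinations; Not known-Psychotic reactions" and "Very rare-Seizures". It also describes an overdose case with psychosis, stupor and unconsciousness. The classification of dropouts in sections 14.1 and 15.2 includes hospitalization and death.

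4. **What does the code tell the clinician?** Everyone takes escitalopram, which section 10.1, item 4.0 describes as open-label. Only memantine versus placebo is hidden. For escitalopram, section 14.1, item 3.0 warns: "Abnormal bleeding, hyponatremia, activation of mania, hypomania, or seizures might occur". Seizures are therefore listed for both drugs. After a seizure, the assignment tells the clinician whether one study drug or two are candidate causes.

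5. **What does not depend on the code?** Stopping study drug, referral and supportive care. The discontinuation criteria are written in terms of symptoms, vital signs, ECG findings and rating scores, and none uses the assignment. For memantine overdose, the plan says that treatment is symptomatic.

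Steps 1 to 3 establish the gap. Steps 4 and 5 bound its consequence.

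**The case against.** The strongest reply is that no acute decision is shown to go wrong. A clinician facing a seizure can presume memantine exposure, stop both drugs and treat the patient. Learning the arm later is then a matter of attribution. No section names a treatment that requires the assignment, and the plan rates seizures on memantine as very rare. This stands, and it is why the consequence is described as limited. It does not supply the missing exception, because the rule itself says that the code is broken to manage the patient.

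A second reply is that the sentence gives a usual order of steps and does not expressly forbid an earlier code-break. That is fair: the text says *after*, not *only after*. Staff who follow it literally would still have nothing to rely on when ratings cannot be had.

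A third reply is that other documents may settle the matter. Section 8.6, item 3.0 refers to a pharmacy application, and section 10.1, item 1.0 lists an attached study plan and assessment schedule. None of these was supplied, so the finding is confined to the application text. If one of them does allow immediate release, it differs from the Decoding procedures paragraph, which would need the same edit.

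A reader might also infer a delay of half an hour to two hours from section 10.1, item 5.0, which says of follow-up visits "Each visit will last approximately 30 minutes" and of the final visit "The last visit will be approximately 2 hours". The documents do not support that step. These are lengths of whole scheduled visits, not rating times, and nothing ties them to a code-break. Cognitive measures are "repeated at 6 and 12 months, or upon early termination", but the plan does not say that they belong to the final ratings that come before unblinding. Clinician scales alone are at least as natural a reading.

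**Conclusion.** The point holds for the application text. One order is set for every code-break during the trial, emergencies included: decide to discontinue, obtain final ratings, then unblind. There is no exception for a patient who cannot be rated or for a case where rating would delay care. This is a stated rule that serves urgent cases less well than a simple alternative.

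The size is limited. What is delayed is knowledge of whether the patient is on memantine. The number of code-breaks is not given and the delay cannot be quantified. A reader might conclude that emergency treatment itself is held back. The documents do not support that, because treatment, referral and stopping drug can all proceed without the code.

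The conclusion assumes that staff apply the sentence as written and that no unsupplied attachment overrides it.

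**What to change.** Split the Decoding procedures sentence in two.

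- **Emergency.** When the assignment is needed to manage the patient, the pharmacist releases it at once. Final ratings are obtained first only if this is feasible without delaying care. The date, the reason, and the order of rating and code-break are recorded.
- **Non-urgent unblinding after discontinuation.** Keep final ratings first. This suits cases such as side effects that persist despite dose reduction (section 15.2, item 5.1).

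The change takes a clause or two and leaves the design, the significance level and the sample size alone. Its cost is an occasional final rating that is missing or made after the code is known. The statistics section (10.1, item 6.0) already projects 25% dropout, and its mixed models for HAM-D and cognitive scores accept incomplete cases. That allowance does not extend to the chi-square comparison of remission. Recording the order of events lets the analyst identify any rating made after the code was known.

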Diagnosis of MCI. We will conduct consensus meetings to assign patients to diagnostic groups, according to MCI criteria that we have used in prior studies and clinical judgment. MCI criteria are: 1) The patient is neither cognitively normal nor demented; 2) a decline in cognition as reported by the subject or a collateral; 3) cognitive testing shows impairment and corroborates subjective report of decline; and 4) functional activities are not significantly impaired. Subjects will be classified as amnesic type MCI (a-MCI) if they show mild impairment in memory with or without other domains impaired. We will use performances between -1.5 and -2 (SD) below age and education norms on one of two screening memory tests; WMS-IV Logical Memory and WMS-IV Visual Reproduction 164 to denote mild impairment 45,75,165. We chose a -1.5 SD index, as this is most widely used 74 and will be most relevant for comparisons with other studies in the literature. We will stratify the groups by the presence of amnesic MCI (either single or multiple domains).
Age at onset of depression: we will explore the role of age at onset in heterogeneity of MCI and treatment response by stratifying groups by onset before or after age 60, as commonly defined.

Medical evaluation. All subjects will receive an initial medical assessment including a complete physical examination with neurological and neuropsychiatric examinations, electrocardiogram (ECG), and laboratory testing at baseline. These tests are used to rule out new-onset medical illnesses that could account for behavioral and cognitive symptoms. All abnormal physical or laboratory findings will be reported to subjects' primary physicians with the subject's consent. If abnormal physical or laboratory results are considered responsible for depression, the subject will be excluded from participation.

3) Baseline assessment.

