Neuropsychological assessment: Our neurocognitive battery was developed by [name], an Associate Professor of Psychiatry and Chief Psychologist for the Geriatric Psychiatry Division at UCLA. [name] expertise spans the study of depression, dementia and mild cognitive impairment. She applies neurocognitive assessment in randomized clinical trials, and evaluates neurocognitive consequences of treatment using cognitive enhancers. Domains of cognition will be assessed that are likely to show impairment in geriatric depression: (1) selected language functions-phonemic and semantic fluency, confrontation naming; (2) executive functioning (we will include measures of cognitive set-switching and inhibitory control); (3) episodic memory. The primary analyses will focus on immediate and delayed recall indices; (4) information processing

speed and attention, including an indices of complex and sustained attention); (5) visuospatial ability. Most of the measures have 2- 4 alternate forms that will be used to reduce learning bias. In addition to the cognitive outcomes, we will include a brief word reading test, the WAIS-IV Test of Premorbid Functioning (TOPF), a revision of the Wechsler Test of Adult Reading, to estimate an individual's premorbid cognitive functioning. We will conduct a confirmatory factor analysis to assess the goodness of fit of our a priori domain assignments, and use data reduction methods. Each a priori composite domain assignment will focus on memory, executive dysfunction, and processing speed as major components of geriatric depression.

Randomization and stratification procedures: After all screening and baseline test results are reviewed and eligibility criteria are confirmed, medications will be dispensed if patients continue to meet eligibility criteria and have signed the informed consent form. All eligible subjects will be randomized to the EsCIT+MEM or EsCIT+PBO control group using a computer-generated random assignment scheme, which assigned subjects in a 1:1 ratio to each group. The groups will be stratified by the a-MCI status, and by late/early onset.

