Data Analysis. Primary analyses will be carried out on an intent-to-treat basis; additional analyses considering dropout or other observable post-randomization outcomes will make use of an instrumental-variable analysis framework. Data will be examined initially to identify issues such as departures from normality, which would suggest the need for transformations (e.g., logarithmic) and influential observations (outliers). Descriptive statistics will be computed and reported overall and by group. Demographic variables and variables characterizing the course of depression (e.g., age of onset, chronicity, number of episodes) will be screened to determine which have relationships with the outcome variables that would suggest their value as covariates. Variables that demonstrate meaningful associations with outcomes controlling for treatment group and are substantially different across groups are candidates for covariates. Demographic variables, baseline depression, and other potential covariates will be compared between the two groups to help determine if the randomization was successful in making the two groups comparable. Specific analysis plan follows below.

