Hypothesis 1. The primary outcome, namely responder/remitter status, will be compared between the esCIT+MEM and esCIT+PBO groups using chi-square statistics. Days to remission will be analyzed using the Kaplan-Meier survival method with treatment group as a stratification variable using the day on which response was observed as the event indicator. The survival function estimates the proportions achieving the response criterion, while the overall survival curve reflects speed of response. The independent variable is treatment group with two levels. A log-rank test will be used to assess the significance of any difference between treatment arms, and Cox regression to reflect the role of baseline covariates. We will also report the total time spent below the response threshold, compare summary statistics, and patterns of response within the patient over time. Analysis of change over time will be performed using linear mixed model analysis of covariance (SAS PROC MIXED). The linear mixed model permits flexible specification of the covariance structure of the repeated measures within patient, and allows analysis of incomplete cases using maximum likelihood. The outcome measures will be the HAM-D scores as well as cognitive domain scores (i.e. memory, processing speed, executive function) with the baseline rating/score on each domain as a covariate.

Hypothesis 2a. The role of brain neuroimaging biomarkers in variability of treatment response is examined in this Hypothesis. Predictor variables: We predict that baseline measures of neuroimaging biomarkers (white matter hyperintensity, regional gray or white matter volumes, hippocampal thickness and regional FDDNP binding levels) will be related to treatment outcomes. These predictions will be evaluated in the context of the models described above (i.e., general linear mixed model) by adding the posited prognostic variable as an additional predictor. Moderator variables: A limited number of exploratory analyses will be performed to evaluate possible moderators of each treatment strategy. Statistical evaluation of moderators will be done by including the posited moderator variable as an independent variable and evaluating the moderator x treatment group interaction term. Mediator Variables: We will evaluate the variable as a potential

mediator using a principal stratification framework.17,20

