Hypothesis 2b. We will also perform categorical data modeling in a 2 (MCI present/absent) x 2 (treatment group) x 2 (response: remitter/non-remitter) table. Randomized stratification by MCI will ensure balanced ratio of subjects with MCI across treatment groups. We will use the Grizzle, Starmer, Koch (1969) approach to linear modeling as implemented in SAS PROC CATMOD. The hypothesis that there is a MCI effect only in the esCIT+MEM condition is tested by the cognition x drug interaction term. Subsequent linear contrasts will compare cognitive groups within treatment groups. The test of MCI on cognitive domain scores will use an analysis paralleling the analysis of treatment effects noted above (mixed effects model with cognitive domain serving as a repeated measure), but with MCI and treatment defining groups. We anticipate that there will be a main effect of MCI associated with poorer baseline performance, but also a main effect of MCI on change (as indicated by a treatment x MCI) interaction effect. Similar analyses, replacing MCI present/absent by early/late onset, will be performed with age of onset. Significance of the treatment x onset interaction effect will allow us to determine if early or late onset is associated with improved performance.

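### The Hypothesis 1 tests leave out the two factors used to stratify randomisation; using them is a cheap, modest improvement, not the repair of an error

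*Combined protocol and SAP*

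**What the plan says.** **Randomisation.** Section 10.1 item 4.0 (Randomization and stratification procedures), repeated in section 11.1 item 6.0, allocates patients "using a computer-generated random assignment scheme, which assigned subjects in a 1:1 ratio to each group" and adds: "The groups will be stratified by the a-MCI status, and by late/early onset". The onset factor comes from "stratifying groups by onset before or after age 60". No block scheme is given.

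**Hypothesis 1 (section 10.1 item 6.0).** The primary outcome, responder/remitter status, "will be compared between the esCIT+MEM and esCIT+PBO groups using chi-square statistics". Days to remission get a log-rank test in which treatment group is the only independent variable, and "Cox regression to reflect the role of baseline covariates", with no covariate named. The mixed models for HAM-D and cognitive domain scores name only the baseline score.

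**Covariate screen (same item, Data Analysis).** "Variables that demonstrate meaningful associations with outcomes controlling for treatment group and are substantially different across groups are candidates for covariates". No threshold is given for either condition.

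**Hypothesis 2b.** MCI, and then onset in its place, enters a remission model and a mixed model of cognitive domain scores. The purpose is to test interaction with treatment; for remission the hypothesis is that "there is a MCI effect only in the esCIT+MEM condition".

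**The concern.** A design that stratifies on two factors normally carries them into the main comparison. If the factors predict remission in both arms and allocation is blocked within strata, a plain chi-square uses a variance that is too large for the design. It is then conservative and can lose power. The log-rank test behaves in the same way.

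There is some reason to expect prognostic strata. The Background links cognitive impairment to inadequate treatment response, and Specific Aim 2 asks whether MCI predicts as well as moderates response. The documents give no size for either factor.

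A second, smaller matter is the covariate screen. It looks for imbalance between arms, which stratification is meant to remove, and it leaves the choice of covariates until outcomes have been seen.

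**Working it through.** **1. The plan's own figure.** Inputs from the Power analysis: 70% v 40%, 50 completers per arm, two-sided 0.05.
- Pooled rate 0.55. Standard error under the null: sqrt(0.55 × 0.45 × 2/50) = 0.0995.
- Standard error under the alternative: sqrt((0.70 × 0.30 + 0.40 × 0.60)/50) = 0.0949.
- z = (0.30 − 1.96 × 0.0995)/0.0949 = 1.107, so power is 0.866. Exact enumeration gives 0.876 (0.829 with Yates' correction). All exceed 80%.
- 50/(1 − 0.25) = 66.7, so 67 per arm and 134 in total also reproduce.

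**2. Why the chi-square is conservative under blocking.** Assume equal strata, an odds ratio (OR) of 3 per factor, and 55% remission in both arms.
- The four strata then remit at about 29.5%, 55.7%, 55.7% and 79.0%.
- Mean within-stratum variance: (0.208 + 0.247 + 0.247 + 0.166)/4 = 0.217. The chi-square uses 0.55 × 0.45 = 0.2475. The ratio is 0.876.
- The effective cut-off is 1.96/sqrt(0.876) = 2.09, a two-sided level of about 3.6%.

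**3. Simulation of chi-square against CMH.** Prognostic strength, block scheme and late-onset share are not in the documents, so they are assumptions: 50% a-MCI (the share that the Background calls feasible), 50% late onset, permuted blocks of 4 within stratum, 50 per arm, 200,000 trials per scenario. Power is at 70% v 40%; type I error is at 55% v 55%.

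| OR per factor, both arms | Power, chi-square v CMH (%) | Change (points) | Type I error, chi-square v CMH (%) |
|---|---|---|---|
| 1 | 87.6 v 86.9 | −0.7 | 5.6 v 5.3 |
| 2 | 88.3 v 88.4 | +0.1 | 4.9 v 5.1 |
| 3 | 89.1 v 90.4 | +1.3 | 4.1 v 4.9 |
| 5 | 90.2 v 93.1 | +2.9 | 3.1 v 5.0 |

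The 5.6% in the first row comes from discreteness at this sample size.

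**4. Variations on the power change.**
- Only one factor prognostic: −0.5 (OR 1.5), −0.3 (OR 2), +0.4 (OR 3), +1.5 (OR 5).
- a-MCI acting only in the memantine arm (80% v 60%): −0.5 at 50 per arm.
- Simple allocation within strata, OR 1 / 2 / 3 / 5 on both factors: −1.7, +0.2, +2.3, +5.5. The chi-square then runs at 5.2% to 5.4% under the null.
- 134 randomised in blocks of 4, 25% dropping out at random, completers analysed: −0.5, +0.8, +2.3, +4.3.
- 30% late onset instead of 50% (main setting): −0.8, 0.0, +1.1, +2.7.

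**5. Log-rank against stratified log-rank.** Assumed exponential times, 67 per arm, 70% v 40% remitted by week 24, 40% dropout, blocks of 4. For a hazard ratio per factor of 1 / 2 / 3, power is 91.0 v 90.3, 93.0 v 94.5 and 95.6 v 98.4. Type I error at a hazard ratio of 3 is 2.6% v 5.0%. The base value is not meant to match the plan's 0.869, which comes without a hazard ratio or event count and so cannot be checked.

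**6. The covariate screen.** Take *substantially different* to mean a standardised difference above 0.2 (an assumption). In 200,000 simulated trials of 134, neither factor reached it with blocks of 4 or 6. With simple allocation each did in about 26% of trials, and at least one did in about 45%.

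**The case against.** The strongest reply is that the gain depends on effects that the documents do not establish. An OR of 3 on both factors implies control-arm remission running from about 17% to about 65% across strata, and nothing in the text supports so steep a gradient. The documents mainly predict moderation: preferential response to the combination in patients with MCI. In that case the stratified test gains nothing. With one modest prognostic factor it loses a little. All of this stands.

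It is also fair that Hypothesis 2b already places treatment with each factor in remission models named in advance. That covers the cognitive scores in part. It does not supply a Hypothesis 1 treatment test that uses the strata, and it never uses both factors together.

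Two stronger readings are tempting, and the documents support neither:
- A reader might infer that the primary test is invalid or the trial underpowered. It is not: with blocking the test is conservative when the strata are prognostic, with simple allocation it stays near 5%, and the stated power holds.
- A reader might infer that the covariate screen shuts the strata out. It only names candidates. Age of onset is among the variables to be screened, and the text does not say that nothing else may enter. The screen is not tied by name to the Cox or mixed models, and it cannot touch a chi-square test, which takes no covariates.

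**Conclusion.** The mismatch is real. Randomisation uses two factors that the Hypothesis 1 chi-square, log-rank and HAM-D mixed model leave out, and the Cox covariates are not named. Correcting it is worthwhile but not essential.

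Under the plan's 70% v 40% with 50 per arm and blocks of 4, the power gain is about 1 to 3 points if both factors are strongly prognostic in both arms (OR 3 to 5). It is about nil or slightly negative if effects are absent, weak, confined mainly to one factor, or present only in the memantine arm. The loss is at most about 0.8 points with blocks and 1.7 with simple allocation. It is therefore too broad to say that the unstratified tests lose power whenever the strata are prognostic.

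The main other benefit is that type I error returns to about 5% when strata are prognostic and allocation is blocked. Fixing covariates in advance is sound whatever the prognostic strength. Every size given here rests on assumed prognostic strength, block scheme and late-onset share.

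**What to change.** In section 10.1 item 6.0:
- Make the primary remission test a CMH test stratified by a-MCI and onset group, and report the Mantel-Haenszel risk difference.
- Stratify the Hypothesis 1 log-rank and Cox analyses by the same two factors.
- Add both factors to the Hypothesis 1 mixed models beside the baseline score.
- Replace the association-and-imbalance screen with covariates named in advance, and show baseline comparisons descriptively.
- State in advance a fallback to a-MCI alone if any stratum falls below a stated minimum size.
- Say that the stratum is a-MCI as randomised, since Hypothesis 2b is worded as MCI present or absent.
- Restate the power for the stratified test.

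The cost is wording. All variables are already collected and no patients are added. Besides the small possible power loss, strata may be thin. If 30% have late onset, each late-onset stratum expects 0.5 × 0.3 × 134 = 20 patients, and the smallest of the four averages about 18 (5th percentile 12). If 50% have late onset, the smallest averages about 28. The fallback is there for that case.
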